3.2. Statistical Analysis Issues

3.2.1. Strata and Covariates

There is no stratification and covariate analysis planned for this study. However, if there is any stratification and covariate analysis performed in an ad hoc exploratory nature, it will be noted in the final CSR.

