5. GENERAL ANALYSIS METHODS

Continuous variables will be summarized using descriptive statistics including number of subjects (n), mean, standard deviation (SD), median, minimum, and maximum. Categorical variables will be summarized using frequencies and percentages. Percentages will be calculated using the total number of subjects in each treatment group for each applicable population and/or subpopulation, unless otherwise noted.

Number of subjects, minimums, and maximums will be calculated to the same number of decimal places as the source data. Means, standard deviations and quartiles will be calculated to one more decimal place than the source data. Percentages will be calculated to one decimal place. Zero count cells will be displayed as “0” with percentage of (0%). Unless otherwise noted, summaries will be performed by the treatment group (Placebo and RSLV-132 10 mg/kg).

If statistical tests are performed, the tests will be done at the two-sided, 5% significance level to compare Placebo vs. RSLV-132 10 mg/kg, unless otherwise specified. The point estimate and 95% confidence interval (CI) for the treatment differences may be displayed along with the p-value for the treatment comparison. P-values will be presented to three decimal places. P-values < 0.0005 will be presented as < 0.001. P-values greater than 0.999 will be presented as > 0.999.

In the absence of any predefined hypotheses in this study, the general strategy of the analysis will be to examine the data summaries for any trends amongst the treatment groups. No formal hypothesis testing will be carried out. P-values obtained from statistical testing of the analyses will be used for descriptive purposes only.

All data collected in the clinical database will be included in the data listings, as appropriate. Subjects who were randomized and never treated will be accounted for in the data listings.

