9.1. Analysis of Primary Efficacy Endpoints

The primary efficacy endpoints are the improvements from Baseline (Day 1) to Day 85 and Baseline to Day 169 CLASI Activity scores.

CLASI Activity assessment will be performed for each subject at scheduled visits to determine the SLE disease activity for each subject at the visit. The assessment includes each anatomical location. The total score of the Activity subsection (defined as the sum of the scores from each anatomical location) will be used in the summary. The improvements from Baseline (Day 1) to Day 85 and from Baseline (Day 1) to Day 169 in the total activity score will be evaluated as part of the primary efficacy endpoints. Lower score represents less disease activity.

Summary of observed values: Observed values of total Activity score and the change and percent change from baseline at each scheduled visit will be summarized. In addition to the LOCF imputation described below, the primary endpoints (change from Baseline on observed values) will be analyzed using Mixed effect Model Repeat Measurement (MMRM) method. The MMRM model will include the fixed categorical effects of treatment, random effect visit, and treatment-by-visit interaction, as well as continuous fixed covariates of baseline score and baseline score-by-visit interaction. An unstructured covariance structure of random effect will be used for modeling the within-subject errors.

Summary of imputed values: LOCF imputed values and the change and percent change from Baseline (Day 1) in the CLASI Activity total score at Days 85 and 169 and at each scheduled visit will also be analyzed. The two-sample t-test will be used for the treatment group comparison on the change from Baseline.

Summary of non-censored values: Non-censored values and LOCF imputed non-censored values as well as the change and percent change from Baseline (Day 1) in the CLASI Activity total score at Days 85 and 169 and at each scheduled visit will also be analyzed. The two-sample t-test will be used for the treatment group comparison on the change from Baseline. The following values will be censored based on blinded review before database lock:

- a. Values obtained within 60 days of a steroid (systemic/oral/topical but not ophthalmic or inhaled) dose that is increased above baseline for more than one day
- b. Addition of other systemic agents for lupus (such as antimalarials, methotrexate, rituximab, dapsone)

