12. SAP REVISION

Revision Date	Section	Summary of Revision	Reason for Revision
July 6, 2017	2.3.3	Updated Table 1 Study Procedures.	Protocol Amendment 4.0
	2.3.5	Updated that efforts will be made to perform all EOT and EOS assessments outlined in Protocol Appendix A.	Protocol Amendment 5.0
	6.2	Clarify the summaries.	Per sponsor request.
	6.3	Clarify to summarize the major protocol deviations.	Per sponsor request.
	7.1	Added the overall mean for prednisone or equivalent dose.	Per sponsor request.
	7.2	Clarify to summarize the Medical History Body Systems	Per sponsor request.
	9	Remove text “RSLV-132 plasma levels and RNase activity” from Efficacy Analyses.	They are not part of the efficacy analyses.
	9.2.2	No statistical testing will be performed for the imputed values of BILAG-2004 Index Assessment.	Per sponsor request.
	9.2.6	Specify to summarize at Day 169 only.	Per sponsor request.
	9.2.7	Remove text “Fisher’s exact test will be used for the treatment group comparison” under the summary of observed values.	No treatment group comparison will be made on observed values.
	9.3.1	Adding dsDNA as part of the autoantibody profile.	Protocol Amendment 4.0
		Adding a summary for the actual values.	Per sponsor request.
	10.1.2	Adding patient year calculations for the adverse event summary	Per sponsor request.

	10.2.1	Adding grade 3 or higher toxicity summaries for the safety lab data.	Per sponsor request.
	10.2.4	Replace text “Appendix B” with “Appendix A”.	Correct protocol reference.
		Physical exam results will be listed only.	Per sponsor request.
March 10, 2020	3.2.7	Revise baseline definition to consider screening.	Internal document consistency.
	6.2	Removing “plus 1” in the Total duration of infusion (Hours) calculation.	Clarification.
	9.1, 9.2.1, 9.2.3, 9.2.4 and 9.2.5	Adding repeated measurement analysis in addition to the LOCF imputation.	A less biased method by missing data compare to LOCF.
	9.1, 9.2.4, 9.2.7	Add non-censored summaries.	Per sponsor request.
	9.2.6	Include table of Predinsone Equivalent dosing.	Facilitate grouping of corticosteroids.
	10.2.4	Adding Physical Exam summary by categories of Normal/Abnormal (CS/NCS).	To be compliant with FDA ICH E3 guideline and to be consistent with Resolve RSLV-132-04 study.
	11	PK not in scope of SAP.	

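### LOCF and non-censored CLASI changes are compared by t-test without baseline adjustment, although baseline is already an MMRM covariate, and the MMRM wording leaves treatment-by-visit fixed or random

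*SAP*

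**What the plan says.** SAP 9.1 analyses change in CLASI activity in several ways.

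- **Observed values:** an MMRM. The treatment and visit terms are given like this: "The MMRM model will include the fixed categorical effects of treatment, random effect visit, and treatment-by-visit interaction". Baseline then enters the same model in a further clause: "as well as continuous fixed covariates of baseline score and baseline score-by-visit interaction". On covariance the SAP adds: "An unstructured covariance structure of random effect will be used for modeling the within-subject errors".
- **LOCF, non-censored and LOCF non-censored values:** "The two-sample t-test will be used for the treatment group comparison on the change from Baseline". No baseline term appears. The non-censored sets drop values near a steroid increase or after another systemic lupus agent was added.

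Sections 9.2.1 and 9.2.3 to 9.2.5 use the same t-test for SLEDAI-2K, PGA, FACIT-Fatigue and joint count, and refer back to 9.1 for the MMRM. Non-censored CLASI change (9.1) and non-censored FACIT-Fatigue change (9.2.4) get the t-test and no MMRM. The non-censored 50% responder analysis in 9.2.7 uses Fisher's exact test and is not part of this point.

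Section 3.2.1 states: "There is no stratification and covariate analysis planned for this study". Section 5 states: "P-values obtained from statistical testing of the analyses will be used for descriptive purposes only". It also says: "The point estimate and 95% confidence interval (CI) for the treatment differences may be displayed along with the p-value for the treatment comparison". The revision log in Section 12 justifies adding the repeated-measures analysis as "A less biased method by missing data compare to LOCF".

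**The concern.** The plan treats the baseline score as prognostic in one analysis and ignores it in parallel analyses of the same endpoint, without giving a reason. Since p-values are descriptive, the estimated difference and its confidence interval carry the proof-of-concept reading. Leaving baseline out usually widens that interval and lets part of any chance baseline imbalance into the estimate. With about 50 subjects randomized 2:1 and no stratification, such imbalance is to be expected.

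The gap falls in an awkward place. Censoring creates missing values, and the sponsor's stated reason for adding the MMRM was its better behaviour with missing data. Yet the censored sets are the ones without an MMRM.

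Separately, the MMRM sentence can be coded in two ways. Treatment-by-visit follows a term labelled random and has no label of its own, and a single unstructured matrix is assigned both to a random effect and to the within-subject errors. Two programmers could fit different models to the primary endpoint.

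**Working it through.** The documents state no power, SD or correlation, so there is no planned figure to reproduce. The ranges below are assumptions.

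**Inputs.** About 50 subjects at 2:1 (SAP 2.3.6 and 2.3.7), taken as 33 and 17. Post-baseline CLASI visits are Days 29, 57, 85, 99, 113, 127, 141, 155 and 169 (Protocol 12.4 and 12.5), nine in all. Assumed: correlation r between baseline and follow-up of 0.3, 0.5 or 0.7; ratio k of baseline SD to follow-up SD of 0.7, 1 or 1.3, with the follow-up SD set to 1.

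**1. Interval width.** Variance of change is 1 + k² − 2rk. ANCOVA residual variance is 1 − r². The large-sample ratio of widths, t-test to ANCOVA, is √[(1 + k² − 2rk)/(1 − r²)]. For k = 1 and r = 0.3 this is √(1.4/0.91) = 1.24; for r = 0.5, √(1.0/0.75) = 1.15; for r = 0.7, √(0.6/0.51) = 1.08. Simulation at 33/17 (4,000 trials per cell), which counts the degree of freedom lost to ANCOVA, gives these mean width ratios:

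| k | r = 0.3 | r = 0.5 | r = 0.7 |
|---|---|---|---|
| 0.7 | 1.07 | 1.01 | 0.99 |
| 1 | 1.23 | 1.14 | 1.07 |
| 1.3 | 1.43 | 1.35 | 1.29 |

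**2. Chance imbalance.** The SE of the baseline difference is √(1/33 + 1/17) = 0.2985 baseline SD. An absolute difference above 0.3 SD has a 31% chance, and one above 0.5 SD a 9% chance. An imbalance of one SE moves the unadjusted difference, relative to the adjusted one, by (1 − r/k) × k × 0.2985 = (k − r) × 0.2985 follow-up SD:

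| k | r = 0.3 | r = 0.5 | r = 0.7 |
|---|---|---|---|
| 0.7 | 0.12 | 0.06 | 0.00 |
| 1 | 0.21 | 0.15 | 0.09 |
| 1.3 | 0.30 | 0.24 | 0.18 |

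**3. MMRM wording.** If treatment-by-visit is fixed, the Day 85 and Day 169 contrasts are what the plan wants. The random reading was simulated (600 trials per scenario, SD 6, within-subject covariance taken as known, random treatment-by-visit variance estimated by REML).

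The assumed effect grows linearly from 0 at Day 29 to −4 or −6 at Day 169. As fractions of the Day 169 effect, the nine visits are 0, 0.2, 0.4, 0.5, 0.6, 0.7, 0.8, 0.9 and 1.0, with mean 5.1/9 = 0.567. For −4 the all-visit mean is therefore −2.27, and full shrinkage to that simple average would be 1 − 0.567 = 43%.

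| Within-subject correlation | Day 169, true −4 | Day 169, true −6 |
|---|---|---|
| Compound symmetry, 0.5 | −3.08 (23% smaller) | −5.19 (13.5%) |
| Compound symmetry, 0.7 | −3.28 (18%) | −5.43 (9.5%) |
| Decaying, 0.4 + 0.6·exp(−lag/3), lag in 28-day units | −2.19 (45%) | −3.44 (43%) |

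Day 85 moves the other way: −1.8 to −2.0 against a true 0.4 × −4 = −1.6, and −2.6 to −3.0 against 0.4 × −6 = −2.4. With a constant effect of −4, Day 169 averages −3.91, −4.07 and −4.02 under the three structures, within about 2% of the truth, which is simulation error.

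These MMRM figures apply to CLASI only. They do not carry over to FACIT-Fatigue (two post-baseline visits) or to SLEDAI-2K, PGA and joint count (six).

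**The case against.** Every continuous endpoint named here already has a baseline-adjusted MMRM on observed change, so the t-test can be seen as a second look. It is also valid on average over randomization, p-values are descriptive, and Section 5 only permits intervals without requiring them. The size of the gain is assumed: entry requires a CLASI activity score of at least 10, which truncates the baseline distribution and makes a baseline SD below the follow-up SD plausible. In that case adjustment gains little or nothing. On the MMRM, baseline-by-visit terms and an unstructured within-subject matrix point to the conventional model with a fixed interaction. The shrinkage figures need the unusual reading, a growing effect and a single random-effect variance, whereas the SAP sentence names an unstructured matrix. They illustrate one possible coding.

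Most of this is fair and limits the size of the point. It does not remove it. Section 3.2.5 names LOCF as the rule for missing efficacy data, and 9.1 presents the MMRM as an addition, so the LOCF t-test is not clearly subordinate. No adjusted analysis covers non-censored CLASI or FACIT-Fatigue change. In the least favourable assumed case, ANCOVA costs about 1% in interval width. The contradiction between 3.2.1 and 9.1 is only a matter of wording, but it is real.

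**Conclusion.** The concern holds, as something that should be fixed; it is not a flaw that invalidates the analysis. The t-test comparisons of change pass over a covariate that the plan already collects and uses. The likely cost is precision: 7% to 23% wider intervals with equal SDs, and from 1% narrower to 43% wider over the full assumed range. A one-SE imbalance adds a shift of 0.00 to 0.30 follow-up SD. These figures rest on assumed correlations of 0.3 to 0.7 and SD ratios of 0.7 to 1.3. The omission matters most for non-censored CLASI and FACIT-Fatigue change, where no adjusted estimate exists. The MMRM wording affects results only if treatment-by-visit is coded as random and the effect changes over time. In the scenarios examined, the Day 169 contrast then shrinks by 9.5% to 45%.

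**What to change.** 1. In SAP 9.1, 9.2.1 and 9.2.3 to 9.2.5, replace the t-tests on change from baseline (LOCF and non-censored) with ANCOVA of change on treatment and baseline score. Report the adjusted difference with its 95% confidence interval. The t-test may be kept as a sensitivity analysis.
2. Restate the MMRM in 9.1: fixed categorical effects of treatment, visit and treatment-by-visit; fixed covariates of baseline score and baseline-by-visit; unstructured covariance for the within-subject residuals; LS-mean differences at Days 85 and 169. Nine visits give 9 × 10/2 = 45 covariance parameters for about 50 subjects, so a fallback covariance structure and a degrees-of-freedom method should be named as well.
3. Run the same MMRM on the non-censored CLASI and FACIT-Fatigue values.
4. Amend 3.2.1 to acknowledge the covariates used in Section 9.

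The cost is SAP wording and a few lines of code. No new data, visits or subjects are needed, and ANCOVA uses one extra degree of freedom.

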### 6.3 Subject Exclusion Criteria

The following will exclude potential subjects from the study:

1. severe, active CNS involvement at Screening;

2. severe renal involvement (urine protein/creatinine ratio of >200 mg/mmol, or an estimated creatinine clearance of <30 mL/min) at Screening;
3. use of cyclophosphamide within 3 months of Baseline;
4. use of background medications within 1 month of Baseline in excess of:
  - a. mycophenolate mofetil > 3 g/day;
  - b. azathioprine > 200 mg/day;
  - c. methotrexate > 25 mg/week;
  - d. hydroxychloroquine > 400 mg/day;
  - e. prednisone (or equivalent) > 15 mg/day;
5. use of an intravenous corticosteroid “pulse” within 2 months of Baseline;
6. use of an intramuscular steroid injection within 1 month of Baseline;
7. use of rituximab within 6 months of Baseline;
8. use of belimumab within 3 months of Baseline;
9. acute infection or history of acute infection within seven days prior to Baseline;
10. positive viral load test for hepatitis B, C or HIV at Screening;
11. receipt of an investigational product within 3 months of Baseline or five half-lives (whichever is longer);
12. positive pregnancy test at Screening or at Baseline;
13. female subjects currently breast feeding at Baseline;
14. inability or unwillingness to comply with study restrictions, return for follow up appointments, or other considerations, in the opinion of the Investigator, which would make the candidate unsuitable for study participation.

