### 7.3 Concomitant Medications

Subjects entering the study who had no changes to their SLE medications in the previous 30 days prior to the Baseline visit shall remain on the background medications at the same doses throughout the study. With the exception of decreases in OCS, no changes in lupus medications shall be permitted during the study, including the addition of topical steroids or topical tacrolimus, except for the rescue of a lupus flare.

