### **7.5 Treatment of Flares**

Investigators should treat lupus flares as they deem appropriate with the minimum amount of corticosteroid necessary and should return the subject to baseline steroid dose as quickly as medically reasonable. Should a subject require more than steroids for a lupus flare, investigators should treat as necessary and notify the medical monitor.

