Summary of non-censored values: Non-censored values and LOCF imputed non-censored values as well as the change and percent change from Baseline (Day 1) in the FACIT-Fatigue Scale total score at Days 85 and 169 and at each scheduled visit will also be analyzed. The two-sample t-test will be used for the treatment group comparison on the change from Baseline. The following values will be censored based on blinded review before database lock:

- a. Values obtained within 60 days of a steroid (systemic/oral/topical but not ophthalmic or inhaled) dose that is increased above baseline for more than one day

- b. Addition of other systemic agents for lupus (such as antimalarials, methotrexate, rituximab, dapsone)

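### The steroid censoring rule in SAP 9.1, 9.2.4 and 9.2.7 has a duration condition that, read literally, lets a one-day IV dose or a single IM injection through

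*SAP*

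**What the plan says.** SAP 9.1 defines a set of non-censored summaries for the CLASI activity score and introduces the criteria with "The following values will be censored based on blinded review before database lock". Rule (a) removes "Values obtained within 60 days of a steroid (systemic/oral/topical but not ophthalmic or inhaled) dose that is increased above baseline for more than one day". Rule (b) is "Addition of other systemic agents for lupus (such as antimalarials, methotrexate, rituximab, dapsone". SAP 9.2.4 (FACIT-Fatigue) and SAP 9.2.7 (CLASI 50% responders) repeat both rules, including the condition "dose that is increased above baseline for more than one day".

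On steroid use during the study, Protocol 7.3 bars changes to lupus medication "except for the rescue of a lupus flare" (steroid decreases are also allowed). Protocol 7.5 says "Investigators should treat lupus flares as they deem appropriate with the minimum amount of corticosteroid necessary". Neither section, nor SAP 2.3.4.2, limits the route or duration of a flare steroid.

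On steroid use before the study, Protocol 6.3 excludes "use of an intravenous corticosteroid “pulse” within 2 months of Baseline" and "use of an intramuscular steroid injection within 1 month of Baseline". The synopsis lists the same two exclusions. Neither carries a minimum number of days, and no reason is given for either.

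**The concern.** The SAP does not state the purpose of the non-censored summaries, but the two rules make it evident: to show these endpoints without scores obtained under added steroid or added systemic lupus therapy. They are the only planned analyses of CLASI activity, FACIT-Fatigue and the responder rate that deal with rescue at all. The observed-value MMRM and the plain LOCF analyses apply no such censoring.

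Rule (a) sorts exposures by how many days the dose was raised, with no reference to route or amount. Read as written, it keeps scores that follow a one-day IV dose or a single IM injection and discards scores that follow a two-day oral increase of any size. Rule (b) does not close the gap, because it concerns agents other than steroids. The protocol permits flare steroid by any route, so the case can arise. At stake is whether these summaries do what they were added to do, and whether the blinded review has a rule it can apply without improvising.

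**Working it through.** There is no planned figure to reproduce: SAP 2.3.7 sets the sample size of about 50 by precedent, without an effect size, SD or power. The check applies the rule as written to the visit schedule and then does simple arithmetic on arm sizes.

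**Inputs.** CLASI visits after Baseline: Days 29, 57, 85, 99, 113, 127, 141, 155 and 169 (Protocol Appendix A). Primary time points: Days 85 and 169 (SAP 9.1). Look-back: 60 days, read here as the 60 days after the steroid. Allocation: 50 subjects at 2:1, so about 33 active and 17 placebo.

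**Step 1: which visits the rule reaches.** A visit on day v is censored if 0 ≤ v − p ≤ 60 for steroid on day p and the dose was raised on more than one day.

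| Steroid | CLASI visits in the period | Censored as written |
|---|---|---|
| One day, Day 71 | 85, 99, 113, 127 | 0 of 4 |
| Two days from Day 71 | 85, 99, 113, 127 | 4 of 4 |
| One IM injection, Day 150, counted as one day | 155, 169 | 0 of 2 |
| Two-day oral increase, Days 110–111 | 113, 127, 141, 155, 169 | 5 of 5 |

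The Day 150 injection falls 169 − 150 = 19 days before the Day 169 score, inside the 1-month interval that the entry criteria use for the same kind of exposure. The oral increase falls 169 − 111 = 58 days before Day 169, and that score is removed.

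**Step 2: how much of the schedule is exposed.** Steroid on Days 25–85 (85 − 60 = 25) bears on Day 85, and steroid on Days 109–169 (169 − 60 = 109) bears on Day 169. Each range is 61 days, so 122 of 169 days, or 72%. On any of those days a one-day dose censors neither primary value at present and would censor one if the duration condition did not apply to it. This counts calendar days; it does not estimate how many subjects would be affected.

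**Step 3: what closing the gap would change, observed non-censored values.** Assume that all 17 placebo subjects have a value at the visit and that a censored subject leaves the denominator. (SAP 9.2.7 uses the actual number at each visit for observed values and does not restate this for non-censored values.) With r responders, removing one of them changes the rate by r/17 − (r − 1)/16 = (17 − r)/272:

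- r = 1: 16/272 = 5.9 percentage points
- r = 4: 13/272 = 4.8 percentage points
- r = 8: 9/272 = 3.3 percentage points

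For the mean CLASI change, removing a subject with change d when the other 16 average m moves the placebo mean by (d − m)/17, about 0.06 points per point of difference.

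**Step 4: the same under LOCF.** If the score after the injection is S and the last uncensored score before it is P, censoring replaces S by P and moves the placebo mean by (P − S)/17. The sign depends on whether P is above or below S. A subject who was already a responder at P stays one, and the responder rate does not change.

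**The case against.** Several objections stand and limit the point.

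- **Pulse is not defined.** A pulse given over two or more days meets the duration condition and is already censored. A reader might infer that IV pulses escape the rule altogether; only one-day dosing does.
- **An IM injection is ambiguous.** The rule speaks of dose, not exposure, and the documents show no recording convention. A blinded review could decide that a long-acting injection raises the dose for more than one day. The omission is therefore not certain for IM steroid, but the text does not settle it either way, and that is itself a reason to write it down.
- **The entry criteria are not analysis rules.** They select patients and give no reasons. A reader might infer that the protocol declares these exposures to be confounding and that the SAP contradicts it. Neither document says so.
- **A duration threshold can be a sensible choice.** Sparing trivial one-day oral or topical changes is defensible, and the fix keeps that. The SAP gives no reason for applying the same allowance to parenteral steroid.
- **The consequence is limited.** The non-censored summaries are supplementary, SAP 2.3.7 and 3.2.3 plan no formal hypothesis testing, and SAP 5 treats p-values as descriptive.

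A reader might also infer a bias toward no difference, on the argument that the less effective arm has more flares and more rescue. The documents do not support that. They give no flare rate, rescue rate or steroid effect; flares need not be cutaneous; steroid may be given for other reasons; and step 4 of the working shows that under LOCF the effect can be nil or reversed.

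**Conclusion.** The concern holds in a limited form. As written, rule (a) does not censor a one-day IV dose or, on a literal reading, a single IM injection, while it censors a two-day oral increase of any size. This sits badly with the evident purpose of the summaries and with the intervals in the entry criteria, but it is an inconsistency of approach only.

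Size and direction cannot be derived from the documents. The figures of 5.9, 4.8 and 3.3 percentage points are illustrations for one placebo responder dropped out of 17, with 1, 4 or 8 responders and complete data; they apply to the observed non-censored responder rate and say nothing about how often this would happen. It would also be wrong to conclude that every CLASI result is affected: the observed/MMRM and plain LOCF analyses do not use rule (a) and do not change.

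**What to change.** In SAP 9.1, 9.2.4 and 9.2.7, apply the duration condition to oral and topical steroid only, and add a sentence to this effect: *any IV or IM steroid administration above baseline, including a single one, censors values in the same 60-day period.* Use identical wording in all three sections and apply it in the blinded review before lock. This changes an analysis rule only and has no bearing on how flares are treated.

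The drafting cost is one sentence in three places. The review would need medication dates, which SAP 8.1 refers to, and route, which rule (a) already needs in order to exempt ophthalmic and inhaled steroid. The downside is some additional censored values; how many is unknown, because no rescue rate is given.
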